Opioid-related side effects (nausea/vomiting, pruritus, urinary retention, and respiratory depression) were evaluated in all patients daily by nurses until hospital discharge. Patients were questioned regarding occurrence of nausea/vomiting and pruritus. Urinary retention was defined as need for reinsertion of a urinary catheter or straight catheterization after Foley catheter removal. Opioid-specific respiratory depression was defined as prolonged tracheal re-intubation secondary to hypercarbia (arterial blood gas analysis) and/or escalation of respiratory support following extubation thought to be secondary to hypercarbia.

Prior to hospital discharge, patients completed the Revised American Pain Society Outcome Questionnaire, which evaluates subjective experiences of pain following surgery.¹⁴

Power Analysis/IRB Termination

Recent clinical research indicates that when comparing two different intraoperative anesthetic techniques in patients undergoing cardiac surgery, a reduction in postoperative morphine requirements during the initial 24 h from a median of 10 mg to 6 mg was observed.¹⁵ With a

one-sided significance level of 0.05 and anticipated 5 mg mean difference (standard deviation of 8 mg), calculated power was 96% for 120 patients total (60 per Group). Initial IRB approval was for study inclusion of 120 patients (60 per Group).

Interim analysis of data for presentation in abstract form yielded statistically significant differences between the two Groups regarding primary and secondary outcomes. Thus, on 9/21/2020 the IRB chose to permanently close the study for enrollment because “the primary end point of this study had been met with statistical significance with fewer number of subjects than what was originally planned”.

Statistical Analysis

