Variables were summarized as mean \pm SD for normally distributed continuous variables, median (25th-75th percentile) for continuous variables with evidence of non-normality or for ordinal variables, and frequency counts and percentages for categorical variables. For the primary outcome (amount of postoperative morphine use) and secondary outcomes (i.e. pain scores, patient satisfaction), comparisons between the treatment Groups were performed using the Wilcoxon rank-sum test (otherwise known as the Mann-Whitney U test). For side effects (secondary outcomes) and other categorical variables, comparisons were made using the chisquared test. However, if there was an expected cell count of <5 , then Fisher’s exact test was utilized.

For pain medication and pain score data, differences between treatment Groups were calculated along with 95% confidence intervals (CIs) using the cendif command in Stata, based on the Hodges-Lehmann method and consideration of all pairwise differences between the two

sets of observations. In addition, box plots were generated for pain scores, stratified by treatment Group and time. As a sensitivity analysis, and to obtain an overall estimate of treatment effect on pain, mixed-effects models were fit (Appendix 2).

Statistical significance was defined as a two-tailed $p < 0.05$ based on tests of superiority; no formal adjustment for multiple testing or interim looks was made. Statistical analyses were performed using Stata 16 (StataCorp LLC, College Station, TX).

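### The stated 96% power is for a one-sided comparison of means, but the primary outcome is judged by a two-tailed Wilcoxon test; at the two-tailed level the same inputs give about 92% for a comparison of means

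*Combined protocol and SAP*

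**What the plan says.** In the combined protocol and SAP, the section Power Analysis/IRB Termination states: "one-sided significance level of 0.05 and anticipated 5 mg mean difference (standard deviation of 8 mg), calculated power was 96% for 120 patients total", that is, 60 per Group. It motivates the effect size with cited research in which "a reduction in postoperative morphine requirements during the initial 24 h from a median of 10 mg to 6 mg was observed".

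The Statistical Analysis section describes the analysis. For the primary outcome, 24-hour postoperative morphine equivalents, "comparisons between the treatment Groups were performed using the Wilcoxon rank-sum test". The threshold is set near the end of that section: "Statistical significance was defined as a two-tailed" p < 0.05, for superiority.

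No power figure is given for a two-tailed test or for the Wilcoxon test, and nothing explains why the planning level and the inferential level differ.

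**The concern.** The planning calculation and the analysis differ in two ways.

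- **Sidedness.** Power was computed at one-sided 0.05. Significance is declared at two-tailed 0.05, which puts 0.025 in each tail and is harder to reach.
- **Test.** Power was computed for a difference in means with a common SD. The primary comparison is rank-based, and its power depends on the shape of the outcome distribution, which the plan does not give.

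Because 96% is the only power figure in the document, a reader may well attach it to the test that decides the trial. What is at stake is the accuracy of that figure: the chance of missing the planned effect is larger than the roughly 4% it implies if the comparison is of means at the two-tailed level. The type I error of the stated two-tailed rule is not in question here.

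**Working it through.** **Inputs**, all from Power Analysis/IRB Termination unless noted: mean difference 5 mg; SD 8 mg; 60 per Group; alpha 0.05, one-sided for planning and two-tailed for analysis (Statistical Analysis). No dropout allowance is stated, and none is needed to reproduce the figure.

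**Step 1. Reproduce the stated power.**
Standard error of the difference = 8 × √(2/60) = 1.461 mg. Noncentrality = 5 / 1.461 = 3.42, with 118 degrees of freedom.
One-sided 0.05: critical t = 1.658; noncentral t power = 96.1%. The normal approximation gives Φ(3.42 − 1.645) = 96.2%. The plan's 96% is reproduced.

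**Step 2. Same inputs at the two-tailed level.**
Critical t = 1.980; noncentral t power = 92.4%. The normal approximation gives Φ(3.42 − 1.960) = 92.8%. Neither rounds to 96%, so the stated figure is specifically the one-sided one. Type II error rises from 3.9% to 7.6%.

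**Step 3. Where the two levels would disagree.**
At SD 8 mg and 60 per Group, the smallest significant observed mean difference is 1.658 × 1.461 = 2.42 mg one-sided and 1.980 × 1.461 = 2.89 mg two-sided. A difference between these values passes at the planning level and fails at the inferential level. These are t-test thresholds; the Wilcoxon test has no exact counterpart in mg.

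**Step 4. Is the sample size short?**
Not on these inputs. For 90% two-sided power in a comparison of means, 55 per Group suffices (90.1%; 54 gives 89.6%). Holding 96% at the two-sided level would need, by the normal approximation, 2 × (1.960 + 1.751)² × (8/5)² = 70.5, so 71 per Group (142 in total).

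**Step 5. Power of the Wilcoxon test.**
This needs a distribution. The group means and the shapes below are assumptions; the plan gives only 5 mg, SD 8 mg and the cited medians. The figures come from simulation with 40,000 replicates and 60 per Group, using the normal approximation to the rank-sum test.

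| Assumed data | Wilcoxon, two-sided | t-test, two-sided |
|---|---|---|
| Normal, 5 mg apart, SD 8 mg | 91.2% | 92.5% |
| Gamma, means 11 and 6 mg, SD 8 mg | 99.8% | 90.9% |
| Gamma, means 17 and 12 mg, SD 8 mg | 96.8% | 91.9% |
| Lognormal, medians 10 and 6 mg, log-SD 0.7 (pooled SD 8.4 mg) | 97.3% | 93.9% |
| Lognormal, same medians, log-SD 0.8 (pooled SD 10.8 mg) | 92.1% | 84.4% |
| Lognormal, same medians, log-SD 1.0 (pooled SD 17.8 mg) | 77.2% | 60.2% |

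For normal data, a separate calculation using the asymptotic relative efficiency 3/π gives 91.3%. The one-sided Wilcoxon figure on normal data is 95.4%. So, for normal data, sidedness accounts for most of the gap (96.1% to 92.4%) and the change of test for about one further point (92.4% to 91.2%).

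**The case against.** The case for leaving the text alone is about weight, not arithmetic.

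- **The basis is disclosed.** The one-sided level, mean difference and SD stand in the same sentence as the 96%, so a careful reader can see that it is not a two-tailed figure. This stands. It shows that nothing was hidden, but it does not supply the missing figure.
- **Only one rule governs inference.** The one-sided level appears only in the power calculation, so the two levels never compete in the analysis, and the band from 2.42 to 2.89 mg illustrates the difference rather than showing harm. This also stands. The mismatch is between a planning assumption and the decision rule, and the rule actually used is the stricter one.
- **Sizing on means and analysing on ranks is common.** It costs about one point on normal data. In the gamma cases that keep exactly 5 mg and SD 8 mg, the Wilcoxon test has more power than the stated 96%. The 77% case requires a pooled SD more than twice the plan's. This is fair: the skewed cases show that Wilcoxon power is undetermined by the plan, not that it is low.
- **The trial is over.** The section records that "on 9/21/2020 the IRB chose to permanently close the study for enrollment", so no restatement can alter sample size or conduct. This is true, and it limits the remedy to the record. The record should still state the power that belongs to the declared significance level.

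**Conclusion.** The inconsistency is real. The 96% is right for a one-sided 0.05 comparison of means and is not the power under the two-tailed rule in the Statistical Analysis section. On the plan's own inputs, two-sided power is 92.4% for a comparison of means and about 91% for the Wilcoxon test if the data are normal. With skewed data, Wilcoxon power could lie on either side of these values, depending on a shape and spread that the plan does not state.

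The effect is modest. Power remains above 90% for a comparison of means and for normal data, the sample size was adequate on the stated inputs, and this mismatch does not raise type I error. All figures are for the planned 120 patients. Enrolment closed early and the document does not give the number enrolled, so power at the achieved size cannot be computed from it.

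**What to change.** Keep the 96% as the original one-sided calculation and add one sentence after it in Power Analysis/IRB Termination:

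> At the two-tailed 0.05 level used for inference, 60 per Group, a 5 mg mean difference and an SD of 8 mg give about 92% power for a comparison of means (about 91% for the Wilcoxon rank-sum test if data are normal).

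A short clause saying that Wilcoxon power depends on the outcome distribution, and may be higher or lower with skewed data, would complete it.

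The cost is that sentence and a slightly less favourable stated power. No patients are added, no analysis changes, and the design history is preserved.
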